5. TTE
6. Blood sample for future research

Endpoints

Primary safety endpoints:

1. Arrhythmia requiring medical therapy or therapy with temporary pacemaker
2. Bleeding requiring transfusions as a direct result of the cooling catheter insertion or secondary to resulting coagulopathy
3. Clinically important bloodstream infection, as confirmed with 2 positive blood cultures, or suspected sepsis in the absence of positive blood cultures with a sequential organ failure assessment (SOFA) score >2
4. Hypokalemia with potassium levels below 3.0mEq/L, not secondary to other identifiable causes

Secondary endpoints:

1. Hemodynamic changes during intervention period – Cardiac output/Cardiac Index, PCWP, SVR, mixed venous oxygen saturation (MVO₂), cardiac power index
2. Cumulative vasopressor and inotrope dose requirements (i.e. number of vasoactive and/or inotropic drugs used)
3. Echocardiographic % change in ejection fraction at 18-24 hours (from baseline)
4. In-hospital all-cause mortality

Procedures

Patients admitted to the Coronary Care unit (CCU) at the University of Chicago will be screened by the study investigators and the cardiology fellow on the CCU rotation. Patients meeting the inclusion criteria, as defined previously, will be identified and randomized after informed consent within 12 hours of presentation. Patients will be randomized to either TH plus standard medical care or to standard medical care alone. A pulmonary artery (PA) catheter will be placed at the bedside or in the Cardiac Cath lab if difficult anatomy is anticipated. As mentioned earlier, placement of a PA catheter is part of the standard of care for management of cardiogenic shock. Currently, patients who are admitted to the University of Chicago CCU with cardiogenic shock routinely undergo placement of PA catheter by the cardiology fellow in the CCU or in the cardiac cath lab. Data from the PA catheter is vital in initiating vasopressors/inotropes, assessing the response to the therapies, and possible need for escalation of therapy (i.e. mechanical support). In this study, patients in each arm will undergo PA catheter placement.

Cooling will then be initiated and maintained using FDA approved ZOLL (Chelmsford, MA) Intravascular Temperature Management (IVTM™) system with the ZOLL Quattro cooling catheter. The ZOLL IVTM along with the Quattro cooling catheter are currently FDA approved for use in cardiac surgery patients to achieve and maintain normothermia during surgery and in recovery and to induce, maintain, and reverse mild hypothermia in neurosurgery patients during surgery and in recovery [11]. The IVTM is not currently FDA approved to achieve therapeutic hypothermia in cardiogenic shock. The use of the cooling catheter and the temperature management system will be off-label for this study. Notably, although not FDA approved for this purpose, current AHA practice guidelines recommend therapeutic hypothermia with a goal temperature of 32°C to 34°C for 12 to 24 hours in patients successfully resuscitated after cardiac arrest as a Class I recommendation if the arrest is from VT/VF and as Class IIb recommendation for CA from other nonshockable rhythms. The European Resuscitation Council guidelines for resuscitation recommend therapeutic hypothermia for all comatose survivors of CA regardless of initial rhythm

The ZOLL 9.3 French Quattro® catheter is inserted into the central venous system via the femoral approach by personnel certified to insert central venous catheters. Placement of the ZOLL catheter is identical to central venous line insertion, such as triple lumen insertion for

administration of medications or a dialysis catheter for temporary dialysis. After successful insertion of the cooling catheter, it will be connected to the Thermogard XP® thermal regulation system. The Quattro® catheter functions as both a central venous triple lumen catheter as well as a cooling catheter. Cooling is achieved by circulating normal saline in a closed system through the catheter. The flow and temperature (range 4°C to 42°C) of the circulating saline serves as the heat exchange mechanism and is controlled by the external Thermoguard® thermal regulation system. The temperature is measured and adjustments are made by the thermal regulation system to automatically maintain target temperature. The target temperature is achieved within 2-3 hours of initiation of TH. Rewarming is accomplished using the same balloon catheter system and heat exchange occurs without infusion of any saline or fluids into the patient. In clinical trials, intravenous catheter based cooling system has been shown to achieve target temperature faster and maintain target temperature with more precision.^{12,14,15}

Medical therapy in both intervention and non-intervention groups will be based on the current recommendations for management of cardiogenic shock. This includes inotropic therapy (i.e. dobutamine or milrinone) for cardiac support, vasopressor therapy (i.e. norepinephrine, dopamine, phenylephrine, epinephrine) to achieve target blood pressure (mean arterial blood pressure \geq 60 mmHg), diuretics for volume removal, and mechanical circulatory support as clinically indicated. All patients included in this study will have pulmonary artery (PA) catheters inserted within 12 hours of randomization via either the internal jugular or femoral venous approach to monitor real-time hemodynamics. The clinicians in the CCU will use the data from PA catheters (cardiac output, mixed venous saturation, systemic vascular resistance, etc.) to guide therapy for both the intervention and non-intervention groups. The primary investigator of this study ([name]) will have no role in the clinical management of the patients.

Laboratory, echocardiographic, and hemodynamic parameters will be obtained for patients prior to randomization, near the end of 24 hour cooling therapy, and after 48-96 hours post-randomization. Core temperature will be measured via either thermal tip at the end of a transurethral urinary catheter or endotracheal temperature probe in intubated patients. Rewarming will be accomplished at 0.3°C per hour until temperature reaches 37°C.

Target Enrollment and Study Duration

In this initial pilot study, we anticipate enrolling 20 patients to the study, 10 randomized to standard medical therapy and 10 patients randomized to standard medical therapy and 24 hours of TH. We anticipate completing enrollment within 6 months.

Statistical Methods

The three-dichotomous primary endpoints will be analyzed using a two-sample independent proportion test or a Fisher's exact test with a Bonferroni method continuity correction for multiple endpoints. Furthermore, numerical secondary endpoints will be presented as either

mean \pm standard deviation or median (interquartile range) based upon the distribution of the data. In addition, all numerical secondary endpoints will be assessed using two independent t tests or Mann-Whitney U test for comparisons. Categorical variables will be tested with chi-square tests of association or Fisher's exact tests. Differences will be considered significant using an alpha value of 0.05 for a two-sided test. Analyses will be performed using STATA MP Version 14 (College Station, TX).

Potential risks and benefits to subjects

A. Benefits:

There is mounting evidence that TH has positive effects on cardiac function. Multiple studies have suggested that TH may offer particular benefit in cardiogenic shock. In this prospective trial, the patients will be randomized to TH or standard medical care using simple randomization. With TH, we expect increased cardiac output, increased contractility, lower SVR, and higher cardiac power index which will lead to improved hemodynamics and potentially decreasing pressor requirements.

B. Risks:

Anticipated adverse events that could possibly occur during the study include, but are not limited to:

1. *Risks associated with TH*
 - a. Shivering
 - b. Arrhythmia
 - c. Coagulopathy with or without clinically significant bleeding
 - d. Hyperglycemia
 - e. Hypothermia
 - f. Electrolyte abnormalities
 - g. Infections
2. *Risks associated with cooling catheter insertion*
 - a. Bleeding
 - b. Infection
 - c. Vascular injury

Mitigating Risks associated with TH:

Shivering is the most common risk associated with TH. Shivering is a normal physiological response to cooling as it allows the body to expend energy and generate heat. This leads to increasing metabolic demands and subsequent oxygen consumption. Various strategies can be used to combat shivering and have these have been well described in the literature. In patients that are intubated, the most common means of combating shivering is a combination of benzodiazepines, opioid analgesics, and/or neuromuscular blockade.¹⁶ In awake patients, combination of meperidine and warming of skin with air-warming products such a 'Bair Hugger

blanket' (3M, St. Paul, MN) hugger' are utilized.¹⁷ Meperidine is the most beneficial agent to prevent shivering and previous studies have demonstrated significant lowering of the shivering threshold with meperidine.^{17,18} Given that intravascular cooling therapy is common in multiple ICU settings, including the cardiac care unit (CCU), protocols are already in place for the management of shivering, with an institutional-approved anti-shivering protocol often used in patients undergoing TH.¹⁸ In the event of persistent shivering despite therapy with intravenous sedatives, anesthetics (i.e. propofol or meperidine) and/or paralytic agents in intubated patients, the TH protocol will be stopped and patients will be rewarmed to normothermia.

Therapeutic hypothermia may potentially increase the risk of arrhythmias and will be evaluated in this trial. Bradycardia is expected with TH. In the previously published studies, the reduction in heart rate is not significant enough to cause hemodynamic compromise.^{9,17,19} However, if a patient is noted to be persistently bradycardic, with signs or symptoms requiring temporary pacemaker insertion, the TH protocol will be stopped. Bradycardia requiring temporary pacing will be considered an adverse event of cooling if the patient did not have underlying conduction system disease (i.e. first or second degree AV block) prior to cooling. In such cases, patients will be rewarming to normothermia per the rewarming protocol currently in place for intravascular cooling of critically ill patients.

In addition to bradycardia, ventricular arrhythmias are potential adverse effects of TH. While ventricular arrhythmias have been reported with TH, data from trials suggests that there is no demonstrable increase in risk of ventricular arrhythmias in patients undergoing therapeutic hypothermia.^{24,25} Importantly, patients in cardiogenic shock have a high risk of developing ventricular arrhythmias either due to ischemia or underlying myocardial scarring. All ventricular arrhythmia episodes requiring intervention will be recorded. If arrhythmia is deemed to be as a result of hypothermia and alternative explanations have been exhausted, the patient will be rewarming to normothermia per the rewarming protocol.

Another risk associated with TH is mild coagulopathy. Temperatures below 33°C have been associated with mild platelet dysfunction in vitro. However, the risk of bleeding with mild TH (32-34°C) is minimal and none of the trials of TH in cardiac arrest or stroke have demonstrated increased risk of bleeding.^{20,21} TH has also been used safely in patients with ischemic stroke who are treated with tPA.²² Based on the currently published data, the risk of bleeding with TH is minimal. Bleeding adverse events will be classified using the GUSTO bleeding criteria.²⁶ In patients who develop moderate bleeding deemed to be a direct result of TH, initial conservative measures of simple transfusions will be implemented. However, if bleeding does not respond to these conservative measures or progresses to severe bleeding, the TH protocol will be stopped and patients will be safely rewarmed.

Hyperglycemia is common during TH as lower temperatures decrease insulin secretion and increase insulin resistance. Many patients with heart failure and cardiogenic shock have concomitant diabetes and glucose control can often be difficult to achieve in these critically ill patients. Clinically significant hyperglycemia will be defined as glucose level exceeding 200mg/d requiring continuous insulin infusion in patients without a diagnosis of diabetes mellitus. Hyperglycemia in patients with diagnosis of diabetes mellitus, or hyperglycemia as a result of other identifiable causes (i.e. administration of steroids, adrenal derangements) will not be considered as a result of TH. In patients who develop hyperglycemia requiring continuous insulin infusion as a direct result of TH, the patient will be treated expectantly and hyperglycemia will be recorded as an adverse event. During TH period, blood glucose will be measured at least hourly during TH, especially in patients receiving intravenous insulin, and during rewarming, when glucose levels can fall.

Hypothermia will lower serum potassium levels, primarily by promoting inward cellular potassium flux, although hypothermia also induces a mild diuresis with concurrent electrolyte wasting. Serum electrolytes will be measured at regular intervals (every 4–6 hours). Potassium will be repleted to maintain levels above 3.5 mEq/L. Rewarming reverses the potassium flux and increases serum levels, so repletion will be held 4 hours before rewarming begins. Clinically significant hyperkalemia is unusual in patients with preserved renal function. In patients with hypokalemia not due to other identifiable causes (diuretic administration, adrenal derangements, etc.), potassium supplements will be administered as per standard of care. Hypokalemia with potassium levels below 3.0mEq/L not secondary to other identifiable causes in patients undergoing TH will be considered an adverse event.

The target temperature of 32-34°C will be achieved using the intravascular cooling catheters. The body temperature will be recorded every 1-2 hours as per the CCU policy in the TH group (as well as the control group). The time spent in the therapeutic window will be recorded and reported. Any deviations outside of the range, specifically $<32^{\circ}\text{C}$ lasting >5 minutes will be reported as an adverse event.

Mitigating Risks associated with cooling catheter insertion:

The risks associated with insertion of a cooling catheter are the same as insertion of any central lumen catheter. These include, but are not limited to, bleeding, infection, and vascular injury. Previously published studies have quoted risk of localized hematomas at 4.7% and risk of vascular injury (most frequently due to inadvertent arterial puncture) at $<1\%$.²³ Incidence of line-associated blood stream infection has been reported as 80-189 episodes per 100,000 patient years.²³

Insertion of a central venous catheter is standard of care in patients in cardiogenic shock to allow for administration of inotropes/vasopressors. The ZOLL Quattro catheters include three standard

central venous catheter infusion lumens to allow for administration of these vasoactive medications. Therefore, patients randomized to TH arm will not need an additional central venous line. Rather, insertion of a cooling catheter will serve the purpose of initiation and maintenance of TH while also allowing for administration of drugs via the infusion lumens. The risk associated with cooling catheter insertion is not expected to be higher than insertion of a standard central venous line.

C. Monitoring of Safety:

During the intervention period, participants will be monitored by physicians, nurses, and technicians in accordance with standard medical care. This includes 24-hour monitored telemetry, with measurement of heart rate, blood pressure, oxygen saturation, and respiratory rate. Real-time hemodynamic monitoring will be measured using pulmonary artery catheters. Blood glucose and electrolyte measurements will be performed as per protocol for patients undergoing therapeutic hypothermia, and correction of abnormalities will be performed by the treating team. Shivering will be monitored by the treating nurse, per ICU protocol, and will be reported to the treating team. TH will not influence the clinician's medical decisions – any medical or mechanical intervention necessary based on clinical status will be allowed.

D. Data Safety Monitoring Board:

Adverse events will be reviewed by the Data Safety Monitoring Board as described below. The study will be halted upon the discovery of unanticipated adverse device events that present a significant or unreasonable risk to subjects enrolled in the study.

The DSMB will meet (in person or via telephone conference) a minimum of 3 times:

- after treatment of the first 4 subjects (2 in the TH arm and 2 in the control arm)
- after treatment of the first 10 subjects (5 in the TH arm and 5 in the control arm)
- at the conclusion of the study

In addition, the DSMB may convene additional meetings if necessary to ensure the ongoing monitoring and safety of the subjects treated with therapeutic hypothermia (TH). A copy of the DSMB charter is located in Appendix 2.

We will collect all treatment emergent and serious unsolicited adverse events during the index hospitalization. A treatment emergent adverse event is any untoward medical occurrence associated with the use of therapeutic hypothermia, whether or not considered related. The DSMB will be informed of expected adverse events, such as shivering, bleeding, and bradycardia, that result in termination of the protocol. Additionally, any unexpected adverse events while undergoing TH will be reported to the DSMB, whether deemed related to TH or not. All adverse event details will be provided to the DSMB prior to the meeting with ample time allowed for analysis. This will include details of the individual adverse events as well as the PI's analysis related to causality, severity and frequency. The DSMB will be responsible for

confirmation of the PI's assessment of all adverse events and final adjudication of all adverse events.

The DSMB will include the following individuals who have agreed to serve on it:

- [name] (University of Chicago Medicine – Section of Cardiology)
- [name] (Inova Health System – Section of Cardiology)
- [name] (University of Chicago Medicine – Section of Cardiology)

Payment to Subjects

Participants will not receive monetary compensation for their participation in this study. The cost of the TH catheters, thermal regulation system and associated monitoring will be part of the study costs and patients will not be charged for these services.

Informed Consent

Informed consent for the study will be obtained from the patient if possible, or the medical decision maker in the event that the patient is incapable of making informed decisions. Due to the nature of the study, we expect that the patient's clinical status will preclude consent directly from the patient. We anticipate that a majority of the consents will be obtained from family and medical decision makers. Once the referring physician has given approval and solicited a patient's or decision maker's interest, a co-investigator will approach and discuss the possibility of participating in this research protocol. The co-investigator will discuss the background and significance of the study, the inclusion and exclusion requirements, and why they are suitable for participation. The study will be summarized for the subject. They will also be informed that they may withdraw at any time during the study without influencing their medical care. The potential participant, including decision maker, will be given the opportunity to ask questions.

Confidentiality

A study file containing all study related information will be kept by the primary investigator in a file cabinet within a locked office or on an encrypted electronic file. Each subject enrolled will have their own file including: study ID number, physician's consent, clinical data as described in Methods, the original signed consent form, proof of eligibility, and any other forms or information.

Protection of Special Populations

Patients younger than 18 years or older than 89 years will be excluded. Additional exclusions will be made as described in Methods. No group of patients will bear disproportionate risk or burden. This includes all eligible Medicare and Medicaid beneficiaries and will not discriminate any patient on the basis of gender, age, disability, and racial or ethnic background. As such, we believe that the results obtained from this study will be generalizable to the Medicare and Medicaid beneficiary population within our specifically stated inclusion/exclusion criteria.

References

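### Primary endpoint 1 does not clearly count VT/VF ended by a shock alone, and it omits TH-arm arrhythmia resolved by rewarming alone

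*Combined protocol and SAP*

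**What the plan says.** The first primary safety endpoint (Endpoints section, item 1) is "Arrhythmia requiring medical therapy or therapy with temporary pacemaker". It is not defined further.

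The subsection on mitigating risks associated with TH handles arrhythmia in three ways:

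- **Recording.** "All ventricular arrhythmia episodes requiring intervention will be recorded". The same paragraph gives the reason to expect such events: "patients in cardiogenic shock have a high risk of developing ventricular arrhythmias either due to ischemia or underlying myocardial scarring". No rate is given.
- **Arrhythmia attributed to TH.** "If arrhythmia is deemed to be as a result of hypothermia and alternative explanations have been exhausted, the patient will be rewarming to normothermia". This rule mentions neither a drug nor a pacemaker.
- **Bradycardia.** For a persistently bradycardic patient "with signs or symptoms requiring temporary pacemaker insertion, the TH protocol will be stopped".

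Allocation is non-blinded (Methods, Patient Population), with 10 patients planned per arm (Target Enrollment and Study Duration). The DSMB has final adjudication of adverse events (Data Safety Monitoring Board section; Appendix 2), but neither place gives a scoring rule for endpoint 1.

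**The concern.** An endpoint defined by treatment received is only as complete as its list of treatments. This list has two entries. It omits cardioversion, defibrillation and resuscitation, and these are not named as arrhythmia treatments anywhere else in the documents. It also omits rewarming, which is the protocol's own response to an arrhythmia attributed to cooling.

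Two things are at stake. First, VT/VF ended by a shock alone may be left out of the primary safety count, or counted by one assessor and not by another who knows the allocation. Second, an arrhythmia resolved by rewarming alone is lost from the TH arm only, because controls are not cooled. The first loss can fall on either arm. The second lowers only the TH count, in a trial whose stated purpose is to assess the safety of TH.

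The endpoint also does not require the arrhythmia to be new or worse, so one already under treatment at entry could count in either arm.

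**Working it through.** The plan gives no event rate, effect size or power for this endpoint, so there is no figure of its own to reproduce. The check is first of wording, then of size.

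**Step 1. Which events score?**

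| Event | Endpoint 1 | Ventricular recording rule | Arm |
|---|---|---|---|
| Arrhythmia needing an antiarrhythmic drug, with or without a shock or rewarming | Counts | Recorded if ventricular | Either |
| Bradycardia needing a temporary pacemaker | Counts | Not ventricular | Either |
| VT/VF ended by a shock alone | Natural reading: no. Broad reading: yes | Recorded | Either |
| Arrhythmia attributed to TH, resolved by rewarming alone | Not a named treatment | Depends on whether rewarming is an intervention | TH only |

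Two features favour the narrow reading in row 3. Endpoint 1 names pacing beside medical therapy, which would be redundant if medical therapy already covered electrical treatment. The Monitoring of Safety section also sets medical apart from mechanical intervention. One feature favours the broad reading. In Procedures, the paragraph that opens "Medical therapy in both intervention and non-intervention groups will be based on the current recommendations for management of cardiogenic shock" goes on to include mechanical circulatory support.

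**Step 2. Weight of one event.** With 10 per arm, 1/10 = 10 percentage points.

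**Step 3. Can one event change the planned test?** Statistical Methods allows Fisher's exact test with a Bonferroni correction at two-sided 0.05. It speaks of three primary endpoints, while the Endpoints section lists four. The level is therefore 0.05/3 = 0.0167 or 0.05/4 = 0.0125. Two-sided p-values at 10 v 10, TH events first:

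- 6 v 0: 2 × C(10,6)/C(20,6) = 2 × 210/38,760 = 0.0108. Significant at both levels.
- 5 v 0: 2 × C(10,5)/C(20,5) = 2 × 252/15,504 = 0.0325. Significant at neither.
- 8 v 1: 2 × (45 × 10 + 10)/C(20,9) = 920/167,960 = 0.0055. Significant at both.
- 7 v 1: 2 × (120 × 10 + 45)/C(20,8) = 2,490/125,970 = 0.0198. Significant at neither.

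At these margins one unscored TH event reverses the result. Away from them it does not: 4 v 0 (p = 0.0867) and 3 v 0 (p = 0.2105) are both non-significant even at 0.05.

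**Step 4. Illustration with assumed rates.** All rates and loss shares here are assumptions. Power is the exact power of Fisher's test at 0.0125, found by enumerating binomial outcomes. Take true rates of 60% TH and 20% control.

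- No loss: difference 40 points, power 12.9%.
- 20% of events unscored in both arms (shock only): 0.60 × 0.8 − 0.20 × 0.8 = 0.48 − 0.16 = 32 points, power 7.4%.
- 40% of TH and 20% of control events unscored (shock plus rewarming): 0.60 × 0.6 − 0.20 × 0.8 = 0.36 − 0.16 = 20 points, power 2.1%.

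Over the five pairs of rates tried (50, 60 and 70% v 20%; 50 and 60% v 10%), the 40%/20% loss cuts a true difference of 30 to 50 points to 14 to 28 points. Power is low throughout, so the main harm is a distorted count, not a lost test.

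**The case against.** The strongest reply has four parts.

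**The term is undefined; shocks are not excluded.** This is correct, since the Procedures text permits a broad reading. But a primary endpoint that scores the same shock as an event or a non-event, depending on the assessor, still needs a definition.

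**The rewarming gap is narrow.** Attribution to TH comes only after other explanations are exhausted. Rewarming at the stated 0.3°C per hour takes (37 − 34)/0.3 = 10 hours to (37 − 32)/0.3 = 16.7 hours, if that rate also applies after early stopping. An arrhythmia serious enough to end cooling may well need a drug or pacing in that time, and would then count. This stands as a limit on frequency, which is unknown.

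**The events remain visible.** Ventricular episodes needing intervention are recorded. The DSMB is told of expected events that end the protocol. A life-threatening arrhythmia fits the serious adverse event definition in Appendix 2, Table A, and goes to the FDA within 48 hours under Table C. This stands: the loss is to the primary endpoint, not to safety review.

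**Nothing is decided on the count.** This is a 20-patient pilot with no success threshold or stopping rule tied to endpoint 1. This too stands, and it lowers the severity.

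A reader might also infer two stronger points that the documents do not support. One is that bradycardia leading to rewarming escapes the endpoint. The bradycardia stopping rule presupposes an indication for a temporary pacemaker, and endpoint 1 counts arrhythmia requiring one, so those patients already qualify. The other is that the rule on prior conduction disease contradicts endpoint 1: "Bradycardia requiring temporary pacing will be considered an adverse event of cooling if the patient did not have underlying conduction system disease". That sentence governs attribution to cooling, whereas endpoint 1 is an all-cause count compared between arms. The two can coexist.

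**Conclusion.** The concern holds as a moderate one. Endpoint 1 probably leaves out VT/VF ended by a shock alone, and certainly does not say whether it counts. It also leaves out arrhythmia resolved by rewarming alone. The shock gap can affect either arm and is not shown to favour TH. The rewarming gap can lower only the TH count, but how often it would do so cannot be estimated from the documents.

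The firm measure of size is 10 percentage points per uncounted event, given the planned 10 per arm. The reversals of significance show what one event can do at the margin; they are not forecasts. The attenuated differences and power figures rest wholly on assumed rates and loss shares.

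**What to change.** Reword endpoint 1 with a closed list, in line with the intervention trigger already used for recording: *New or worsened arrhythmia after randomization requiring any of the following interventions: drug therapy, electrical cardioversion or defibrillation, resuscitation, or temporary pacing.*

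State that ventricular episodes recorded under the risk section are scored against this definition. Tabulate each component by arm. Report TH-arm arrhythmias that led to early rewarming without another qualifying treatment on a separate line, and show the endpoint with and without them. Only one arm can have such events, so they should not sit unmarked inside the compared endpoint.

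The cost is one protocol sentence and matching tick-boxes on the case report form. Event rates may look slightly less favourable. The change concerns counting only and leaves clinical management as it is.
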